### **Study Procedure:**

We will be administering a brief survey to willing participants after they provide electronic consent. If a participant decides to participate, they will receive a paper survey to complete, or they can complete the survey online via an anonymous REDCap survey link.

The Isha Foundation (which is responsible for the Inner Engineering Online Course) has agreed to send participants an email which contains detailed instructions on how to perform the IEO intervention after the electronic consent has been signed. The Isha Foundation receives the participating employee emails from the company, as they are the primary instructors for the intervention.

Subjects will be randomized following the consent into two groups.

**Group 1** will be asked to complete the Inner Engineering Online course which includes completing 7 meditation and yoga course modules in a duration of 30 days. They will be given an IEO activity diary and will be asked to keep a track of their progress. The activity diary will be collected from them on a

weekly basis for 30 days.

After 4 weeks (i.e., 30 days) they will be administered the same set of survey questionnaires which was asked before the intervention was administered. All communications will be conducted electronically or via phone.

**Group 2** will be asked to read a book or journal of their choice for 30 minutes at a time for 30 days. They will also be asked to complete a reading log every day to keep a track of their progress every day for 30 days.

Once 30 days is over they will be asked to complete the IEO intervention, which includes practice of meditation and yoga daily for another 30 days while maintaining an IEO activity diary. Group 2 will be asked to complete set of questionnaire at baseline, 30 days and after 60 days.

Surveys will be administered at two time points for group 1 at baseline and at 30 days, whereas three time points for group 2 that is baseline, 30 days and 60 days.

Apart from the surveys, the participants are advised to maintain a reading log or an activity diary for each week. These documents will be collected electronically, either via direct online submission or a scanned copy to be uploaded and sent to a redcap survey link at the end of each week. In order to account for national holidays and personal circumstances, participants may submit their activity diaries and/or reading logs within 2 weeks of the 30 day and 60 day time point.

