### **Randomization:**

Participants will be randomized into one of the two groups using [Simple Randomization Technique] by REDCap. Participants will be randomized into:

1. Intervention Group: Participants will receive the Inner Engineering Online Intervention for a total of 30 days (4 weeks)
2. Control Group: Participants will read a book/journal of their choice for 25 minutes each day for a total of 30 days (4 weeks)

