#### **Analysis of Aim 2:**

Given the continuous nature of the scales used to assess stress, burnout and measures of well-being, differences between groups will be assessed with a parametric or non-parametric t-test. Although we expect that randomization should account for any differences between baseline characteristics, unadjusted and adjusted linear regression may be utilized in order to account for differences that persist. Our primary analyses will be assessed using intention-to-treat principles. In order to assess whether there are differences between baseline and at six weeks, we will employ the use of paired t-tests as appropriate.

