### B5. POSSIBLE RISKS AND ANALYSIS OF RISK/BENEFIT RATIO

**Potential physical risks of the study interventions:** The IEO intervention is simple and only involves meditation & yoga practices. As such, there are no physical risks expected with the IEO intervention. Similarly, by assessing stress, burnout or well-being measures; we do not anticipate any risk of physical harm to any of the research subjects.

**Potential psychological risks:** It is possible that there could be psychological or emotional risk to subjects in this study if they were to become aware of their performance in assessments and more so than they would be if they were not participating in the study. Subjects will not be given the scores of their assessments, but if they were to become aware of a decline in their performance this could be stressful or disconcerting to the subject. Additional counseling regarding any psychological or emotional distress stemming from this will be provided by the Principal Investigator at the request of the subject.

**Risk of breach of confidentiality:** As with any research study, there is a small risk associated with a breach of confidentiality. All research staff for this trial has been extensively trained in how to handle confidential data and how to minimize the possibility of this risk. To mitigate this risk, electronic data and that on paper will be kept in confidential, locked file cabinets and secure offices and/or on password-protected computers. Subjects will also be assigned a unique study ID to minimize this risk.

**Risk/Benefit Ratio:** IEO intervention has no expected risks and the knowledge gained could potentially lead to studies that focus on improvement of stress, burnout and overall long-term well-being of general population. Research team members will attempt to mitigate any of the possible risks described above; therefore, we believe the risk/benefit ratio is in keeping with allowing conduct of the trial.

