### B8. DATA SECURITY

All electronic data will be stored in REDCap and/or on password-protected servers behind the BIDMC firewall. Any data collected on paper will be stored in locked file cabinets or in secure offices. All data would directly be entered into REDCap database.

No individual identifier will be obtained from the company other than the email for sending surveys. Each subject will be assigned a study-specific ID number. A crosswalk between the participants and their study IDs will be maintained on password-protected computers by members of the research team. At no time will this crosswalk be shared outside the study team.

All data would be directly entered into REDCap database and at the completion of the study all identifiable will be deleted and data analysis will occur using only the participant's study ID, to further ensure confidentiality of their responses

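### The survey link is called anonymous, which contradicts the coded data described under Data Security; built that way, the paired tests of Aims 2 and 3 could not be run

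*Combined protocol and SAP*

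**What the plan says.** The Study Procedure part of section B3.A is the only place that describes how survey answers are captured. Participants may use paper, or "they can complete the survey online via an anonymous REDCap survey link". It does not say how either kind of response is tied to a person or a visit. Surveys are repeated: baseline and day 30 for Group 1; baseline, day 30 and day 60 for Group 2; then a follow-up round 30 days later.

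The analysis of Aim 2 compares groups with a t-test, allows regression adjustment as an option, and for change over time states that "we will employ the use of paired t-tests as appropriate". The analysis of Aim 3 repeats that sentence.

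Section B8 describes something other than anonymous data. "Each subject will be assigned a study-specific ID number", and "A crosswalk between the participants and their study IDs will be maintained on password-protected computers by members of the research team". Email is the identifier used to send the surveys: "No individual identifier will be obtained from the company other than the email for sending surveys". After identifiers are deleted at study completion, "data analysis will occur using only the" participant's study ID. Section B5 repeats the unique ID, and the Randomization section has REDCap allocate the arms.

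**The concern.** A paired test needs each person's two answers side by side, and so does regression on the person's own baseline score. A crosswalk joins people to study IDs. It joins answers to people only if each answer bears the ID, and an answer from a truly anonymous link does not. Emailing such a link does not change this, because the email shows who was invited and not who gave which answers.

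So the two descriptions cannot both be right. If the Study Procedure wording governs the REDCap build, the within-person analyses are lost. Aim 3 suffers most, because it concerns change within one group after cross-over. The feasibility purpose suffers too: the sample size section says the data will be used to power a larger trial, and the SD of change and the between-visit correlation cannot be estimated from unlinked answers. If section B8 governs, employees would be told that a link is anonymous while the team holds a re-identification key. The first failure is permanent, since answers collected without an ID cannot be matched later.

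**Working it through.** **What each analysis needs, against what the text provides**

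| Planned analysis | Needs arm | Needs within-person link | Possible with a truly anonymous link? |
|---|---|---|---|
| Between-group t-test, Aim 2 | yes | no | yes, if the link is arm-specific |
| Paired t-tests, Aims 2 and 3 | no, if run within one group | yes | no |
| Regression adjusted for own baseline score (optional) | yes | yes | no |
| SD of change for the larger trial | no | yes | no |

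**Illustration of the loss.** The protocol gives no effect size, SD, correlation or power, so it has no figure of its own to reproduce.

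Inputs from the documents: minimum enrolment 60; two-sided alpha 0.05.

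Assumptions: n = 30 in the group (half of 60, no dropout); equal SD at both visits, taken as 1; correlation r = 0.5, 0.6 or 0.7; 80% power.

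1. True standard error (SE) of the mean change: sqrt(2(1−r)/30) = 0.183, 0.163, 0.141 SD. This holds whether or not the answers are linked, because the same 30 people respond twice.
2. Linked, paired t-test: detectable change ≈ (t for 0.975 + t for 0.80, 29 df) × SE = (2.045 + 0.854) × SE = 0.53, 0.47, 0.41 SD.
3. Unlinked, two visits analysed as independent samples: the analyst must use an SE of sqrt(2/30) = 0.258 SD. The detectable change is therefore 2.002 × 0.258 + 0.842 × true SE. This is 0.517 + 0.154, 0.137 or 0.119, or about 0.67, 0.65 and 0.64 SD. A simulation of the same situation gives values within 0.01 SD of these.
4. Increase in detectable change, unrounded: 0.670/0.529, 0.654/0.473 and 0.636/0.410, or about 27%, 38% and 55%.
5. Actual type I error of the unlinked test: 2 × [1 − Φ(1.96/sqrt(1−r))] = 0.56%, 0.19%, 0.03%. Simulated values are slightly higher, at about 0.7%, 0.3% and 0.08%.

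With a weaker correlation of r = 0.3 the loss is smaller: true SE 0.216, detectable change 0.63 SD linked and 0.70 SD unlinked, type I error about 1.9%.

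**Optional baseline adjustment.** Assume 30 per arm and a true difference of 0.5 SD. Power = Φ(0.5/[0.258 × sqrt(1−r²)] − 1.96). Unadjusted (r = 0 in the formula) this is 49%. Adjusted for own baseline it is 53%, 61% and 77% at r = 0.3, 0.5 and 0.7. That gain is also unavailable without the link.

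**Planning the larger trial.** The variance of change is 2(1−r) in units of the single-visit variance: 1.4, 1.0 and 0.6 at r = 0.3, 0.5 and 0.7. The sample size for a test of mean change scales with this, a 2.3-fold range (1.4/0.6) that unlinked data could not narrow.

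**The case against.** The strongest reply is that the plan, read whole, intends coded data and contains one wrong adjective. Section B8 has surveys sent to individual emails, gives each subject an ID, keeps a crosswalk, and places the study ID with the responses at analysis. Deleting identifiers at completion presupposes that the data were identifiable until then. This stands as evidence of intent. It does not supply the missing step, because no section says that a survey record carries the ID, and the one section on data capture says the reverse.

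A reader might go further than the text allows in four ways:

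- That the plan as a whole cannot support its analyses. Section B8 shows that linkage was intended, the main Aim 2 test needs no within-person link, and adjusted regression is only optional.
- That arm could only be self-reported. The Randomization section states: "Participants will be randomized into one of the two groups using [Simple Randomization Technique] by REDCap". Every survey after baseline follows allocation, so a separate link per arm would carry the arm without identifying anyone.
- That the unlinked detectable change is 0.74 SD. That figure assumes two different samples of 30. Here the same people answer twice, so the true SE is unchanged and the test becomes conservative.
- That the consent form promises anonymity. The consent pages were not available for review, and the consent section of the protocol does not mention it.

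**Conclusion.** The concern holds as an internal contradiction with a real but conditional consequence. The stated capture rule (anonymous link) conflicts with the stated data model (study ID, crosswalk, analysis by ID). If the capture rule is followed literally, the paired t-tests, individual baseline adjustment and the SD of change are lost, while the between-group comparison survives. For within-group change, the detectable effect rises by roughly a quarter to a half for r between 0.5 and 0.7, with type I error below 1%. These figures rest on an assumed 30 people, equal SDs and the assumed correlations. The contradiction does not depend on them. It should be corrected before data collection.

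**What to change.** In Study Procedure, replace the anonymous link with a participant-specific REDCap link that stores the study ID and visit, and state that arm is joined from the REDCap randomisation record. Require the study ID on every paper survey. Describe the data as confidential and coded in both Study Procedure and section B8, and in the consent form if it promises anonymity.

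The cost is a wording amendment and a REDCap setting. The downside is that employees can be told the survey is confidential but not that it is anonymous, which may make some less willing to answer the burnout, depression and anxiety items.

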### B3. DESCRIPTION OF RESEARCH PROTOCOL

#### A. Study Design – Overview, Methods, Procedures

##### Study Overview:

This study involves evaluation of the effects of Inner Engineering Online (IEO) intervention by employing validated questionnaires aiming to measure stress and well-being in the form of a survey to company employees participating in the study.

In order to evaluate this, we randomize the participants into either of the two groups: one who participate in the IEO activities daily for the first 30 days and the other who do not participate in the IEO activities during the first 30 days. We then evaluate stress and burnout along with measures of well-being in these participants using validated electronic instruments at baseline and at the end of the 30 days. This is phase 1 of the study.

For the phase 2, we cross-over the group 2 participants and provide them with the IEO intervention. We follow them through another 30 days and then evaluate measures of stress, burnout and well-being using validated instruments at the end of these 30 days.

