### Consent

Electronic Consent will be obtained following a few screening eligibility questions to ensure study eligibility in willing participants. The study procedures will be described in detail, including the perceived risks and benefits. The electronic consent will emphasize that participation is completely voluntary.

In addition, we will provide contact information for the study team to ensure that all of the participant's questions are answered prior to providing consent. Electronic consent will then be obtained from willing participants prior to initiation of any study procedures.

*Please see the attached electronic enrollment script.*

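### No described instrument asks controls about IEO use in days 0 to 30, and the email that delivers the course instructions is not tied to allocation

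*Combined protocol and SAP*

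**What the plan says.** The design is staged. The Study Overview (B3.A) sets a group doing IEO daily for 30 days against "the other who do not participate in the IEO activities during the first 30 days", and continues: "For the phase 2, we cross-over the group 2 participants and provide them with the IEO intervention". Under Randomization, IEO appears for the Intervention Group only ("Participants will receive the Inner Engineering Online Intervention for a total of 30 days"), while the Control Group reads. Study Procedure gives Group 2's start: "Once 30 days is over they will be asked to complete the IEO intervention", with practice "daily for another 30 days while maintaining an IEO activity diary".

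Study Procedure also covers delivery. The provider "has agreed to send participants an email which contains detailed instructions on how to perform the IEO intervention after the electronic consent has been signed", and "The Isha Foundation receives the participating employee emails from the company". Randomization is then placed after consent. The Consent section (B6) adds: "Electronic consent will then be obtained from willing participants prior to initiation of any study procedures".

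In the first 30 days, controls complete the outcome questionnaires and a reading log. Analysis of Aim 1 plans a deviation proportion and an in-house satisfaction survey. Primary analyses follow intention-to-treat (Analysis of Aims 2 and 3). Sample Size Justification sets a minimum of 60 participants and says that their data will be used to power a larger trial.

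**The concern.** The Aim 2 contrast is IEO against no IEO over the first 30 days. Intention-to-treat rightly keeps every control in the control arm, whatever that person did. If some controls practise IEO early, the between-group difference shrinks. If nobody asks them, the analyst cannot say whether a small difference reflects a weak intervention or an exposed control arm. The same uncertainty passes into the estimates intended for the larger trial. Aim 3 is affected too if the day-30 value is its reference, because that value would already hold some IEO effect.

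The email sentence adds to this. Someone outside the study team sends the instructions, from a list that the company supplies, and the text mentions no allocation information reaching the sender.

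**Working it through.** **1. Is early IEO use by controls captured anywhere?** The described instruments, taken in turn:

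| Instrument (B3.A unless noted) | What it is described as covering | IEO use by controls, days 0 to 30? |
|---|---|---|
| MAAS, PSS, MBI, DPES-Joy, CES-D, anxiety short form | Mindfulness, stress, burnout, joy, depression, anxiety | No |
| Reading Log | Reading | No |
| IEO Activity Diary, Group 2 | The second 30 days | No |
| 30 day Follow Up questions | IEO practice after the study period | No |
| Final Survey | Long-term compliance and impact | No |
| Deviation proportion (B3.B, Analysis of Aim 1) | Deviations, not defined | Not named; could catch use that a control volunteers |
| Satisfaction survey (B3.B, Analysis of Aim 1) | Satisfaction; items not given | Not named |

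**2. Is early use plausible?** Three facts bear on it.
- Interest in IEO is one of the two inclusion criteria (B3.C).
- The company offers the standalone course to interested employees (B2). The text does not say whether an enrolled control can take it in days 0 to 30.
- The email sentence gives no arm and no Group 2 date. Its only time reference, consent, comes before allocation exists.

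**3. Scale.** The minimum of 60 has no effect size, SD, power or dropout behind it, so there is no planned figure to reproduce. What follows is an illustration. Let c be the share of controls using IEO and f the share of the full effect that they gain. Both are assumed.

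- Retained share of the Aim 2 difference = 1 − c·f
- Sample-size ratio for a later trial sized on the diluted difference, at the same SD, power and alpha = 1/(1 − c·f)²

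| c | f | Retained share | Sample ratio |
|---|---|---|---|
| 10% | 1 | 0.90 | 1/0.90² = 1.23 |
| 20% | 1 | 0.80 | 1/0.80² = 1.56 |
| 30% | 1 | 0.70 | 1/0.70² = 2.04 |
| 10% | 0.5 | 0.95 | 1/0.95² = 1.11 |
| 20% | 0.5 | 0.90 | 1/0.90² = 1.23 |
| 30% | 0.5 | 0.85 | 1/0.85² = 1.38 |

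**4. What one question would buy.** Assume 30 controls (60 split evenly, which simple randomization does not guarantee), all of whom answer. Exact (Clopper-Pearson) two-sided 95% limits:

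- 0 of 30 report use: upper limit 1 − 0.025^(1/30) = 11.6%. At full effect the sample ratio is then at most 1/(0.8843)² = 1.28.
- 6 of 30 report use: 7.7% to 38.6%.

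Even a small control arm would therefore put a useful bound on the problem, subject to honest self-report.

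**The case against.** The strongest reply concerns the email. Both arms eventually receive IEO, so a sentence saying that participants are sent instructions after consent can be true of both without simultaneous sending. Consent may set only the earliest time, and the Study Overview, Randomization and Study Procedure sections make the staging plain. This stands. A reader might infer that the protocol contradicts itself, or that controls will get the instructions at day 0. The documents support neither; they show a sentence that leaves the matter open.

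Second, the survey forms, the reading log form and the satisfaction items are not reproduced, so an unseen item could ask about IEO. This also stands, and is why the claim is limited to described instruments. The deviation proportion is partial cover at best: its denominator is required activity, and no source of information on IEO use is named.

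Third, the company course may not be open to enrolled controls in days 0 to 30. That is correct. It is a possible route, not a confirmed one.

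Fourth, the dilution formula applies to any trial with a control arm, and the harm runs one way: a later trial sized on a diluted effect would be too large, not underpowered. If that trial had the same background uptake, the diluted effect would be the right planning value. Fair, but choosing between those cases requires knowing the uptake.

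Last, this is an unpowered feasibility study, and nothing in it promises a contamination measure. That lowers the severity. It does not remove the point, because the stated use of the data is to plan a larger trial.

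**Conclusion.** The point holds as a minor, cheap improvement. On the described instruments, control exposure to IEO in the first 30 days goes unasked. The circumstances make some exposure plausible, and the email wording does not rule out delivery before the cross-over.

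The size cannot be known from the documents. Over assumed uptake of 10% to 30%, with half to all of the effect gained, the Aim 2 difference keeps 95% down to 70% of its size. This rests on assumed uptake and gain, a constant SD, and comparison with a trial planned on the undiluted effect.

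A reader might go further and conclude that Aim 2 is biased. The documents do not show that any control will use IEO early, so the supportable conclusion is that the trial, as described, could not tell.

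**What to change.** 1. **Measure exposure.** Add a short item at the end of the day-30 survey in both arms, after the validated scales so that it cannot affect those answers. For example: *During the first 30 days of the study, did you practise any part of IEO? If so, on about how many days, and where did the instructions come from (study email, company course, other)?* Tie it to the first 30 days, so that a control who answers late does not report phase 2 practice. Keep intention-to-treat primary, and report the number and proportion of controls with any IEO use, with an exact interval, beside the Aim 2 result.

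2. **Reconcile the email sentence with the existing staging.** For example: *The provider sends IEO instructions to Group 1 participants after randomization and to Group 2 participants at the cross-over, using addresses released as each participant becomes due to start.* The survey schedule does not change.

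The cost is one extra self-reported item, which may under-count, and one reworded sentence. If enrolment is rolling, the address releases must be repeated. Releasing addresses by start date also changes the present flow from company to provider. Staging the email would not close the company route, if controls can use it; the survey item would only record that use.
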